6 STATISTICAL CONSIDERATIONS

6.1 Primary Endpoint

The primary endpoint is the rate of Adverse Events/SAEs in Anterior VBT Surgery.

6.2 Secondary Endpoints

The secondary endpoint is change in post-operative Cobb angle compared to pre-operative Cobb angle, measured on coronal radiograph of the spine.

6.3 Statistical Methods

6.3.1 Baseline Data

Baseline and demographic characteristics will be summarized by standard descriptive summaries (e.g. means and standard deviations for continuous variables such as age and percentages for categorical variables such as gender). Categorical data analysis methods such as chi-square will be used for dichotomous variables and repeated measures Anova or t-test for continuous data (such as differences in Cobb angle). Logistic regression analysis will be conducted to analyze various factors associated with adverse events in anterior tethering surgical procedure.

6.3.2 Safety Analysis

The safety endpoint will be factors associated with the adverse events in patients that have undergone Anterior VBT Surgery. Variable reporting for adverse event will be dichotomous. Descriptive statistics will be used to report number and type of adverse events. Further, chi-square or fisher-exact test analysis will be used to identify variables that correlate with adverse events following anterior tethering surgery. Further, logistic regression will be conducted to clarify which variables are associated with adverse outcomes. Odds ratio along with confidence intervals will be reported.

All subjects will begin the safety analysis at Study Day 0 (day of surgery). Intraoperative and post-intervention medical events or signs and symptoms of the complications arising after the start of study intervention will be captured using list of common events associated with Anterior VBT Surgery. Adverse signs, symptoms, and/or laboratory abnormalities already existing prior to the baseline visit will be captured in the medical history assessment.

The date of onset, severity, and end date (if relevant) will be documented.

Medical events resulting from any procedure performed in the study will be collected as adverse events (AEs). The event description, date of onset, end date, severity, and outcome will be documented for the study-related AEs. The frequencies of AEs by type, body system, severity and relationship to study intervention will be summarized. SAEs (if any) will be described in detail. A distinction will be made between those AE/SAEs which are "device-related", those which are "not device-related", and those which are "uncertain to be related". "Device-related" complications will include any events directly related to the integrity, safety, or biomechanics of the PET cord. Device-related AE incidence will be summarized along with the corresponding exact binomial 95% two-sided confidence intervals. 22

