- 5. Associated syndrome, including Marfan Disease or Neurofibromatosis
- 6. Sanders bone age greater than 4
- 7. Thoracic curve less than 35 degrees
- 8. Lumbar curve greater than or equal to 35 degrees
- 9. Unable or unwilling to firmly commit to returning for required follow-up visits
- 10. Investigator judgement that the subject/family may not be a candidate for the intervention

Number Of Subjects

Study Duration

Study Phases:

Screening

Study Treatment

Post-op Follow-Up

The study will be conducted at The Nemours – Alfred I duPont hospital for Children, Division of Orthopedics. Subject inclusion will be based on interest of patients that satisfy the inclusion/exclusion criteria that present to the Orthopedic Clinic. The total study enrollment will be 30 subjects. In the retrospective arm we will aim to enroll all patients who had the tether surgery in the past. The study ends when all patients reach skeletal maturity. Each subject's active participation will last about 5 years after surgery. The entire study is expected to last at least 8 years.

- 1. Screening phase: Subjects will be screened by study staff during a clinical visit in the Orthopedics department. Eligible subjects will be approached and if interested, enrolled during a routine clinical exam.
- 2. Study Treatment: The subject will undergo surgical intervention using accepted standard-of-care anterior approach using the Globus Medical Inc. CreoTM Stabilization System. Vertebral body tethering using screws and Polyethylene Terepthalate cord (Globus Medical, Inc. Reflect/TransitionTM Stabilization System) is investigational.
- 3. Post-operative Follow-up: Subjects will be followed at regular time points at 45 and 90 days post-op during the post-operative phase. Patients will also be seen at visits 180, 365, 730, 1095, 1460, 1825 days post-op during the extended follow-up phase.

Efficacy Evaluations

The primary efficacy evaluation measurement is thoracic Cobb angle (to nearest degree) at the pre-operative visit to Cobb angle during follow-up, especially at two years post-op (POD 730).

Safety Evaluations

We will use phase-specific endpoints to measure safety: 1) Study treatment phase: Any individual-level intraoperative events including neuromonitoring events (loss or change in neurological signaling or function), unanticipated events during surgery, and SAEs.

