3.3.2 Total Number of Study Sites/Total Number of Subjects Projected

The study will be conducted at Nemours – Alfred I duPont Hospital for Children. As this is a registry of an approved device being used in an off-label method, we do not have a maximum number of patients or target enrollment. Based on a broad review of patient visits over the past year, we may expect to enroll up to 15 patients per year. These patients will be followed up clinically until skeletal maturity. The total number of enrolled subjects in both retrospective and prospective arms will be 30.

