8.3 Definition of an Adverse Event

An adverse event is any untoward medical occurrence in a subject who has received an intervention (drug, biologic, or other intervention). The occurrence does not necessarily have to have a causal relationship with the treatment. An AE can therefore be any unfavorable or unintended sign (including an abnormal laboratory finding, for example), symptom, or disease temporally associated with the use of a medicinal product, whether or not considered related to the medicinal product.

We will use the Clavien-Dindo Classification system [47], as well as the Comprehensive Complication Index (based off of the Clavien-Dindo system) [48] to classify and analyze patient adverse events. **Grade I and Grade II events will be considered AEs.** (See Appendix 1 for classification table)

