12 APPENDIX

12.1 Appendix 1: Clavien-Dindo complications classification system (from Dindo, et al.)

Grade	Definition		
Grade I	Any deviation from the normal postoperative course without the need for pharmacological treatment or surgical, endoscopic, and radiological interventions		
	Allowed therapeutic regimens are: drugs as antiemetics, antipyretics, analgetics, diuretics, electrolytes, and physiotherapy. This grade also includes wound infections opened at the bedside		
Grade II	Requiring pharmacological treatment with drugs other than such allowed for grade I complications		
	Blood transfusions and total parenteral nutrition are also included		
Grade III	Requiring surgical, endoscopic or radiological intervention		
Grade IIIa	Intervention not under general anesthesia		
Grade IIIb	Intervention under general anesthesia		
Grade IV	Life-threatening complication (including CNS complications)* requiring IC/ICU management		
Grade IVa	Single organ dysfunction (including dialysis)		
Grade IVb	Multiorgan dysfunction		
Grade V	Death of a patient		
Suffix "d"	If the patient suffers from a complication at the time of discharge (see examples in Table 2), the suffix "d (for "disability") is added to the respective grade of complication. This label indicates the need for a follow-up to fully evaluate the complication.		

^{*}Brain hemorrhage, ischemic stroke, subarrachnoidal bleeding, but excluding transient ischemic attacks. CNS, central nervous system; IC, intermediate care; ICU, intensive care unit.

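### Section 6.3.2 plans logistic-regression odds ratios for unnamed AE risk factors in about 30 patients, with no cap on predictors and no method for sparse tables

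*Combined protocol and SAP*

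**What the plan says.** Section 6.3.2 makes the factors associated with adverse events the safety endpoint and states that "Variable reporting for adverse event will be dichotomous". Factors are first examined by chi-square or Fisher's exact test. Then "logistic regression will be conducted to clarify which variables are associated with adverse outcomes", with odds ratios and confidence intervals. Section 6.3.1 repeats the regression for a set of factors that it does not list. Neither section names a predictor, limits their number, gives an expected AE rate, or says how the model is fitted when data are sparse. Section 6.4 disclaims any power analysis.

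On numbers, the synopsis says "The total study enrollment will be 30 subjects" and section 3.3.2 says "The total number of enrolled subjects in both retrospective and prospective arms will be 30". Section 3.3.2 also says "we do not have a maximum number of patients or target enrollment", and the synopsis adds "In the retrospective arm we will aim to enroll all patients who had the tether surgery in the past".

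On grading, section 8.3 and the SAE definition in section 8.4 say that AEs will be classified and analysed by Clavien-Dindo grade "as well as the Comprehensive Complication Index". Grades I and II count as AEs, and Appendix 1 begins grade I with "Any deviation from the normal postoperative course without the need for pharmacological treatment". Section 6 does not mention the index. Severity appears there only in a frequency summary.

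**The concern.** With about 30 patients, a yes/no AE outcome can be lopsided in either direction. Serious events may be few. An outcome of any AE at all may be close to universal, because grade I is defined so broadly. In both cases a factor can easily split the patients so that one cell of its 2×2 table with the AE is empty. Maximum-likelihood logistic regression, the usual default when nothing else is named, then has no finite estimate (separation): the odds ratio runs to zero or infinity and the usual Wald interval is meaningless. Even when the estimate is finite, it is biased away from the null in samples of this size. An uncapped list of factors makes this more likely, because a model that contains a separating factor is itself separated.

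At stake is whether the risk-factor results can be read at all. A factor could be reported with an enormous odds ratio and no usable interval, or dropped because the software did not converge.

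**Working it through.** **Inputs.** n = 30 (synopsis; section 3.3.2). The documents state no power, event count or effect size, so there is no figure to reproduce. The event count and the number exposed are assumptions, shown as a range.

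**Step 1: one binary factor, no true effect.** With m events and k exposed among 30, the number a of exposed patients with an event is hypergeometric:

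P(a) = C(k, a) × C(30 − k, m − a) / C(30, m).

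A cell is empty when a = 0, a = m, a = k, or a = m + k − 30. Worked cases:

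- m = 3, k = 6: (2024 + 20)/4060 = 50%
- m = 3, k = 15: (455 + 455)/4060 = 22%
- m = 6, k = 6: (134596 + 1)/593775 = 23%
- m = 6, k = 15: (5005 + 5005)/593775 = 2%

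| Events | 3 exposed | 6 exposed | 9 exposed | 15 exposed |
|---|---|---|---|---|
| 3 | 72% | 50% | 35% | 22% |
| 6 | 50% | 23% | 9% | 2% |
| 9 | 35% | 9% | 2% | 0.1% |

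Swapping event and non-event gives the same table, so the rows for 3 and 6 events also serve for 27 and 24.

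**Step 2: several predictors.** This was a simulation of 800 runs per setting with n = 30, a true odds ratio of 2 for the first binary factor, and binary prevalences of 15%, 30% and 30%. It gives the chance of complete or quasi-complete separation at each AE rate:

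| Model | 10% | 20% | 30% | 50% | 80% | 90% |
|---|---|---|---|---|---|---|
| 3 continuous | 14% | 1% | 0% | 0% | 1% | 15% |
| 1 binary + 2 continuous | 51% | 26% | 18% | 24% | 57% | 79% |
| 3 binary + 3 continuous | 82% | 48% | 29% | 25% | 71% | 92% |

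With five predictors, events per variable are 30 × 0.10/5 = 0.6 at a 10% AE rate, 1.2 at 20%, and 3 at best (15 events).

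**Step 3: what a penalised fit changes.** For one binary factor, Firth's method equals adding 0.5 to each cell. Suppose 3 of 9 exposed and 0 of 21 unexposed patients have an AE. The maximum-likelihood odds ratio is infinite. The Firth estimate is (3.5 × 21.5)/(6.5 × 0.5) = 23.2, with a Wald 95% interval of 1.05 to 509. Fisher's test copes with the same table: p = C(9,3)/C(30,3) = 84/4060 = 0.021.

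On bias, take 6 exposed and 24 unexposed, AE risks of 25% and 10%, and hence a true log odds ratio of ln 3 = 1.10. Summing over all possible tables, the mean Firth log odds ratio is 1.12. Maximum likelihood is finite with probability 76%, and its mean in those tables is 1.33.

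**Step 4: enrolment above 30.** With n = 60, 12 exposed, no effect and a binomial event count, the empty-cell chance is 29% at a 10% AE rate and 7% at 20%. A larger cohort reduces the problem but does not remove it at low rates.

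**The case against.** The strongest reply is that the trouble is conditional. Infinite odds ratios are rare for a balanced factor at mid-range AE rates and for continuous predictors alone at rates of 20% to 80%. Several recorded candidates, such as operative time, blood loss and BMI, are continuous. The SAE stopping thresholds (7 of the first 10; more than 50% after 20 cases) show that the plan contemplates event rates well above 3 to 6 in 30. This stands. A reader might infer that unusable odds ratios are the expected result, but with neither rate nor predictors given, the documents support only the range.

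The plan also does not exclude an exact or penalised fit; it leaves the fit open. Fisher's test is already planned and stays valid with empty cells. The primary endpoint in section 6.1 is the AE/SAE rate, and device-related incidence gets exact binomial intervals. All of this stands, so the point is confined to the regression odds ratios and their intervals.

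A reader might also infer that the protocol ignores the complication index, or that the index should replace the yes/no outcome. Section 8 does plan to analyse AEs with the index, so the gap is between sections 8 and 6. Replacement to POD 90 would lose events that matter: section 6.6.2 diagnoses tether failure only after 3 months, and the synopsis places over-correction, implant failure and re-operation in the extended phase.

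Nor is a gain in power assured. In simulations with 15 against 15 patients and a proportional-odds ratio of 4 on worst grade (a proxy for the index), a rank test had 50%, 51% and 52% power, against 28%, 20% and 2% for Fisher on any AE, at baseline any-AE rates of 30%, 60% and 85%. Part of that gap is Fisher's conservatism. Where a factor changed occurrence (10% against 40%) but not severity, the rank test had 47%, chi-square 52% and Fisher 32%.

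**Conclusion.** The concern holds as a cheap improvement to section 6.3.2. As written, the regression can give zero, infinite or inflated odds ratios. For one binary factor in 30 patients with no true effect, the chance of an empty cell runs from 72% (3 events, 3 exposed) to 2% (6 events, 15 exposed), and it is lower still at mid-range rates. Adding predictors can only raise the chance of separation. These figures rest on n = 30 and on assumed event counts and exposure. Section 3.3.2 gives both 30 and no maximum, which must be reconciled. The AE rate, the Fisher tests and the device-related intervals are not affected. Separately, sections 6 and 8 disagree on whether the complication index is analysed, and this needs resolving whatever AE rate occurs.

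**What to change.** In section 6.3.2:

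1. Fit Firth-penalised logistic regression with profile-penalised-likelihood intervals, or exact logistic regression. Use one pre-named predictor per model, list the predictors in advance, and label the results exploratory. Keep Fisher's test.
2. Keep the yes/no analysis for SAEs, device-related events and later events.
3. As a supplement, add a rank-based analysis of the Comprehensive Complication Index to POD 90. A rank method suits the many zero scores that are likely. POD 90 is the natural limit because the recording plan in section 8 captures all AEs only to that day; afterwards it captures SAEs and device-related AEs.
4. Reconcile the two enrolment statements in section 3.3.2.

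The cost is SAP wording and no new data. The statistical price is that no odds ratio is adjusted for other factors. Intervals will also stay wide: penalisation makes the estimates finite and less biased, but it does not add information.

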5.2 Safety Evaluation

Subject safety will be monitored by recording all AEs and SAEs, and will be recorded on the complication form in the patient's study binder. The evaluation of safety is a primary objective of

this research study. There will be a clear classification of "device-related" adverse events. Device-related adverse events are those events directly related to the integrity, safety, or biomechanics of the device components: **PET cord, staples, set screws and vertebral screws.** This can include variables like device breakage or device migration. Other adverse events which are considered not device-related are those that are related to the act of surgery and medical recovery. The type of events will be documented on the CRF.

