6.6.2 Stopping rules for SAEs that are device-related
Definition of Terms:
□ Screw failure – screw and/or centering staple have loosened from the vertebra AND require re- operation
☐ Tether failure – the tether has broken or lost tension. Diagnosed at any time point after 3 months by increased angulation at a disc space on standing PA or increase in disc wedging on side bending x-ray to the side away from the implant. Also, it is only an SAE if noted before maturity AND overall Cobb worsens compared to the first erect measurement
☐ Implant re-operation - any problem with the implant that requires re-operation including re-operation for overcorrection with any of the following: a removal of all or part of the implant, loosening of the tension on the implant, or spinal fusion.

Stopping Points
☐ Screw failure stopping point: 3 of first 5 cases, 5 of first 10, or 25% of patients beyond 20
cases
☐ Tether failure stopping point: 3 of first 5 cases, 5 of first 10, or 25% of patients beyond 20
cases
☐ Implant failure re-operation stopping point: occurs in 4 of first 5 cases or greater than 50% of
cases beyond 10 cases

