7.3 Labeling

The device is part of a commercially marketed system from Globus Medical, Inc. As such the device will be labeled according to manufacturer guidelines and in compliance with 21 CFR 801. Specific device label parameters will be tracked by the study team to comply with FDA standards for investigational device tracking. Those parameters include:

- o Manufacturer of device
- o Model name of device
- o Device Part Number
- o Device Lot Number
- o Unique Device Identification (UDI)
- o Length of PET cord used

All parts of the tethering system (vertebral screws, set screws, staples and PET cord) will be labeled and tracked in the same manner.

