8.4.1 Relationship of AE/SAE to study intervention or device

The relationship of each Event to the study intervention should be characterized using one of the following terms in accordance with NEMOURS IRB Guidelines: **definitely, probably, possibly, unlikely or unrelated**. In this case, the "study intervention" in considered to be the surgical intervention and implantation of the medical device (*Anterior vertebral body tethering surgery under general anesthesia with spinal cord monitoring*). This includes (but is not limited to) induction of anesthesia, incision and surgical approach, device implantation, and recovery. **For each SAE, the PI and Safety Officer will make a case-by-case determination on the relationship of the SAE to the study procedure, which will be documented in the study documents.**

There will be further classification of the Event as either "device-related", "not device-related", or "uncertain to be device-related". Device-related adverse events are those events directly related to the integrity, safety, or biomechanics of the implanted device. This can include variables like device breakage or device migration. Other adverse events which are considered not device-related are those that are related to the act of the surgery and medical recovery (anesthesia, incision and surgical approach, post-operative recovery, etc.). This distinction will be indicated in the study documents. For each Event, the PI and Safety Officer will make a case-by-case determination on whether the Event is "device related", "not device related", or "uncertain". An event which is classified as "device related" will be considered an Adverse Device Effect. Adverse device effects have special reporting guidelines, as outlined below.

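### Section 6.3.2 ties device-related events to the PET cord alone, just before the device-related incidence and its exact CI, although 5.2 lists four components; applied literally, the rate can only be equal or lower.

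*Combined protocol and SAP*

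**What the plan says.** Section 6.3.2 (Safety Analysis) first distinguishes three classes of event: device-related, not device-related and uncertain. It then says that device-related "complications will include any events directly related to the integrity, safety, or biomechanics of the PET cord". The statistic follows at once: "Device-related AE incidence will be summarized along with the corresponding exact binomial 95% two-sided confidence intervals".

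Other sections describe the category more broadly:

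- **5.2 (Safety Evaluation)** applies the same three criteria to the device components, listed as "PET cord, staples, set screws and vertebral screws".
- **8.4.1 (Relationship of AE/SAE to study intervention or device)** says "Device-related adverse events are those events directly related to the integrity, safety, or biomechanics of the implanted device". Classification is made event by event: "For each Event, the PI and Safety Officer will make a case-by-case determination on whether the Event is" device related, not device related or uncertain.
- **7.1** describes the device as the cord used together with screws and staples, and calls that combined use investigational.
- **6.6.2**, under its heading for device-related SAEs, defines screw failure as "screw and/or centering staple have loosened from the vertebra AND require re- operation" and gives it its own stopping point.

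**The concern.** The narrowest description stands beside the only event rate for which the plan specifies a confidence interval. An analyst working from 6.3.2 could reasonably build the numerator from cord events alone. The plan would then disagree with itself: a loosened screw could count toward a device-related stopping rule in 6.6.2 and yet be missing from the device-related incidence in 6.3.2.

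Safety is the primary objective, and what is under study is the whole construct of cord, screws and staples. A device-related rate that covers one component answers a narrower question than its label suggests. Any error runs in one direction only, toward a more favourable rate.

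**Working it through.** **Step 1. Compare the definitions.** The documents state no device-related rate, so there is no figure of the plan's own to reproduce. The check begins with the text.

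| Section | Role | Components covered |
|---|---|---|
| 5.2 | defines the category | cord, staples, set screws, vertebral screws |
| 6.3.2 | describes the category for analysis | cord |
| 6.6.2 | stopping rules, device-related SAEs | screws, staples, tether, implant as a whole |
| 8.4.1 (relationship) with 7.1 | classifies each event | implanted device: cord with screws and staples |

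Sections 5.2 and 6.6.2 are the direct evidence, because each names screws and staples under a device-related label. Section 8.4.1 reaches them through the description of the device in 7.1. Section 7.3 ("All parts of the tethering system (vertebral screws, set screws, staples and PET cord) will be labeled and tracked in the same manner") is a tracking rule and supports the point only indirectly. Section 9.3.2.1 settles nothing, because it lists screw pullout and fracture both under investigational device risks and under ordinary spine surgery risks.

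**Step 2. Direction.** Let *c* be the number of patients with at least one cord event, and *a* the number whose only device event is in a screw, set screw or staple without effect on the cord.

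- Literal 6.3.2 rate: c/n.
- Rate on the 5.2 list: (c + a)/n.
- Difference: a/n, which is never negative.

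The literal rate is therefore equal or lower, never higher.

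**Step 3. Size per patient.** Section 3.3.2 says that there is no target enrollment, but also that 30 subjects will be enrolled across both arms. At n = 30, one such patient is 1/30 = 3.3 percentage points. If the final number differed, it would be 1/20 = 5.0 points at n = 20 or 1/40 = 2.5 points at n = 40 (both sizes assumed).

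**Step 4. Illustration with the plan's own interval.** The exact two-sided 95% limits for x of n are

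- lower = Beta quantile at 0.025 with parameters (x, n − x + 1), or 0 if x = 0;
- upper = Beta quantile at 0.975 with parameters (x + 1, n − x).

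For x = 0 and n = 30 the upper limit is 1 − 0.025^(1/30) = 11.6%. The documents give no expected event rate, so the counts below are assumptions, with c = 0 and n = 30.

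| Anchor-only patients (a) | Literal 6.3.2 | 5.2 list |
|---|---|---|
| 0 | 0/30 = 0% (0 to 11.6) | 0/30 = 0% (0 to 11.6) |
| 1 | 0/30 = 0% (0 to 11.6) | 1/30 = 3.3% (0.1 to 17.2) |
| 3 | 0/30 = 0% (0 to 11.6) | 3/30 = 10.0% (2.1 to 26.5) |

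**The case against.** The best defence is that the broader definition already governs. The verb in 6.3.2 is inclusive and does not limit the category. The three classes named just before it are those of 8.4.1, under which every event is judged against the whole device and the judgement is documented. No separate cord-only coding step appears anywhere. Section 1.2.2 may also explain the wording: the screws and staples are to be placed as in their approved use, and the cord is what replaces the rigid rod.

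Much of this stands. If the recorded 8.4.1 classification feeds the incidence, the understatement is zero. But 6.3.2 never makes that link, and the only description it gives of the category names one component where 5.2 names four.

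A second point also stands. Section 1.2.3 has the cord passing through the screw heads under tension and locked there by set screws, so many anchor failures could count as events of cord biomechanics. The clear omission is confined to anchor events that leave the cord unaffected.

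Three stronger readings are tempting, and the documents do not support them.

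- **That screw and staple failures would go unreported.** SAEs are described in detail, AEs are summarized by type, and the Synopsis lists implant failure on serial x-ray and re-operation among its extended-phase safety endpoints.
- **That the screw-failure stopping point ("Screw failure stopping point: 3 of first 5 cases, 5 of first 10, or 25% of patients beyond 20") bounds the loss.** Under 6.5, meeting a rule halts enrollment; it does not cap what happens later in patients already treated. The rule also counts only re-operated loosening, which is unlikely to leave a tensioned cord unaffected.
- **That the recording plan adds to this understatement.** After day 90 it records only those non-serious AEs deemed device related, so late uncertain ones drop out. That is a separate data-capture matter and does not change the device-related numerator.

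**Conclusion.** The conflict in wording is real and should be corrected. Section 6.3.2 describes the category by the cord alone, while 5.2 and 6.6.2 include screws and staples by name, and 8.4.1 read with 7.1 includes them through the device as a whole.

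The consequence is conditional and limited. It arises only if 6.3.2 is applied literally and at least one patient has an anchor event, no cord event, and no effect of the anchor event on the cord. Each such patient then lowers the device-related incidence by 1/n, or 3.3 points at n = 30. The number of such patients cannot be derived from the documents. A reader might infer that the reported rate will be biased, but the text supports only that it can be understated.

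The overall AE/SAE rate (the primary endpoint in 6.1), the SAE descriptions and the stopping rules in 6.6 do not depend on the 6.3.2 wording.

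**What to change.** Two edits to 6.3.2:

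1. Where the text refers to the PET cord alone, refer instead to the device components, with the list from 5.2: "PET cord, staples, set screws and vertebral screws".
2. Add a sentence stating that the device-related incidence and its exact interval use the classification recorded for each event under 8.4.1 (Relationship of AE/SAE to study intervention or device). Cite the heading, because the number 8.4.1 is also used for the follow-up report.

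The cost is one phrase and one sentence, with no new data collection, and a device-related rate that may look less favourable. The recording of late uncertain AEs should be taken up separately.
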